Prevalence of Albuminuria in patients with Cardiovascular
Disease and
Type 2 Diabetes mellitus in China: a national cross-sectional
study PLACARD

Research Protocol

<< Version 3.1 , October 26, 2023 >>

main researcher: [name]
Team leader unit: Beijing Anzhen Hospital
Sponsor: Heart Health Research Center
Financial Bayer HealthCare Co., Ltd.
Sponsor:

Principal Investigator Statement

I have read the following research protocol:

Research protocol title: Prevalence of Albuminuria in patients with Cardiovascular Disease and Type 2 Diabetes mellitus in China: a national cross-sectional

Version and date: Version 3.1, October 26, 2023

I have read the study protocol and all study documents and agree that they contain all necessary details to conduct the study. I will follow the protocol and complete the research within the allotted time. I will provide a copy of the study protocol and all relevant information to all principals and sub-centre investigators assisting with the conduct of the study. I will discuss the material with them to ensure they fully understand the mission and conduct of the study.

Investigator's signature:

main researcher:

[name] _____
date signature

Research Protocol Overview

Study title	Prevalence of Albuminuria in patients with Cardiovascular Disease and Type 2 Diabetes mellitus in China: a national cross-sectional
Research objectives	
Primary Objective
 
To assess the prevalence of albuminuria in patients who are combined with type 2 diabetes mellitus and different cardiovascular diseases in inpatient and outpatient cardiology departments of secondary and tertiary hospitals in China.
 
Secondary Objectives
 
(1) To evaluate the levels of microalbuminuria and macroalbuminuria of patients with type 2 diabetes mellitus (T2DM) in inpatients and outpatients cardiology departments;
 
(2) To evaluate the prevalence of microalbuminuria and macroalbuminuria in patients with T2DM complicated with different cardiovascular diseases;
 
(3) To evaluate the related influence factors of albuminuria and the treatment patterns of CKD patients and non-CKD patients in cardiology departments;
 
(4) To evaluate the management of risk factors and complications in cardiovascular departments of patients with T2DM complicated with microalbuminuria and macroalbuminuria in different levels of hospitals.
 
Exploratory Objective

	To evaluate the prevalence of retinopathy in T2DM patients with different cardiovascular diseases attending inpatient and outpatient cardiology departments in secondary and tertiary hospitals in China.
Research design	Multicenter, cross-sectional study
Research center	30 medical centers nationwide in China
Research sample	3,000 cases
Study timeline	Expected enrollment date of the first patient is December 2023 Last patient expected completion date is June 2024
Inclusion criteria	
 1. Age \geq18 years old; 2. Diagnosed T2DM combined with \geq1 CVD (hypertension, coronary heart disease, atrial fibrillation, heart failure); 3. During the data collection period, they went to the outpatient clinic of the cardiology department of the research center, or received treatment in the cardiology department; 4. Ability to self-sign informed consent (electronic /paper).
Exclusion criteria	
 1. Pregnant or lactating women; 2. Dialysis patients; 3. Other diseases that lead to elevated albuminuria, such as severe infection, confirmed primary glomerular disease, etc.;

	
4. Malignant tumors being treated (surgery, chemotherapy, radiotherapy or targeted therapy);
 
5. Cachexia (CSS score \geq 5 points);
 
6. Severe liver disease (Child- Pugh grade C) ;
 
7. Participated in an interventional clinical trial in the past three months.

Statistical methods	
The analysis will be performed using SAS 9.4 statistical software. Descriptive statistics will be calculated and reported, including number of observations, means, standard deviations, medians, interquartile ranges for continuous variables, and frequencies and percentages for categorical variables. Percentages will be calculated based on non-missing data unless otherwise specified. The data will be checked for bias and outliers. Conversion will be done as needed. Missing data will be assumed to be missing at random or completely at random, and no imputation will be applied except in special circumstances.

Data collection	Case Report Form (CRF)

1 Introduction and Research Background

1.1 Cardiovascular disease, type 2 diabetes and chronic kidney disease

The association between Cardiovascular Disease (CVD) and Chronic Kidney Disease (CKD) is well established. Traditional risk factors for CVD and CKD are similar, with type 2 diabetes mellitus (T2DM) being the most prevalent risk factor. However, CKD is underdiagnosed and undertreated in patients with CVD. Further understanding of the combination of CKD in CVD patients is important to formulate prevention and treatment strategies for CVD patients and high-risk groups, reduce adverse events in CVD patients, and prevent progression of CKD to End Stage Renal Disease (ESRD).

CVD patients and CVD high-risk patients are high-risk groups for CKD. The Spanish MULTIRISC study showed that about 37% of outpatients with CVD and CVD high-risk patients had CKD¹. T2DM accounts for 25%-30% of outpatients and inpatients in the department of Cardiology, which is an important reason for the high incidence of CKD in the CVD population. Population aging has not only led to an increase in the prevalence of T2DM but also the prevalence of the comorbid CKD. The greatest increase in the prevalence of T2DM has occurred in low- and middle-income countries, where patients with T2DM are also at higher risk of developing CKD. Although the incidence of CVD in T2DM patients has decreased in recent years, T2DM-related renal impairment has not decreased correspondingly. In China, 20%-40% of T2DM patients will progress to CKD, which is the main factor of CKD and ESRD². Globally, more than 50% of patients requiring renal replacement therapy have concurrently T2DM³.

Impaired renal function increases the risk of CVD by 2 to 4 times⁴ and T2DM patients with

CKD live an average of 10–16 years shorter than others⁵. In CVD, urinary protein is strongly associated with an increased risk of developing heart failure, especially in patients with T2DM or CKD or both⁶. A recent large study integrated 4 community-based cohorts and investigated the prognostic value of 12 biomarkers (including urinary protein excretion rate, natriuretic peptide, and troponin) in 22,756 participants. With a median follow-up of 12 years, increased urinary protein excretion was found to be an independent predictor of Heart Failure with reduced Ejection Fraction (HFrEF) and Heart Failure with preserved Ejection Fraction (HFpEF) factors, and for each increase standard deviation in Urinary Albumin/Creatinine Ratio (UACR), the risk of HFrEF increases by 21% and that of HFpEF increases by 33%⁷. Increased proteinuria may reflect elevated levels of endothelial function and inflammation, which is consistent with the widespread microvascular dysfunction and inflammation characterized by HFpEF⁸. Data from the SPRINT study showed that proteinuria had an cumulative predictive value for heart failure risk on the basis of eGFR (estimated glomerular filtration rate)⁹. Decreased renal function is also associated with an increased risk of coronary heart disease. With the eGFR decreased to 60 – 75 mL/min/1.73 m², the incidence of coronary heart disease increased linearly. When the eGFR decreased to 15 mL/min/1.73 m², the risk of dying from coronary heart disease increased threefold¹⁰. In addition, albuminuria can also increase the mortality of non-ST-segment elevation myocardial infarction (NSTEMI) patients¹¹. Even in the absence of decreased eGFR, patients with elevated UACR had significantly higher CKD and CVD risks¹², while lower urinary protein levels improved cardiovascular and renal outcomes in T2DM patients¹³. Therefore, the 2021 European Society of Cardiology (ESC) cardiovascular prevention

guidelines recommend screening for the progression of atherosclerotic disease and renal disease in all CKD patients with or without T2DM, including monitoring changes in urinary protein¹⁴.

CKD prevention in T2DM patients is to identify high-risk groups and intervene in related risk factors, such as strict control of blood pressure, rational control of blood sugar, adjustment of unhealthy lifestyle, and adoption of kidney protective therapeutic measures¹⁵. To prevent CVD events in CKD patients, treatment should be initiated in the early stages of CKD. The presence of proteinuria is a predictor of CKD progression and is associated with increased CVD risk, regardless of normal eGFR. According to the current recommendations of the Kidney Disease: Improving Global Outcomes Working Group, the treatment of patients with T2DM should include lifestyle modification as the basic treatment, followed by renin-angiotensin system(RAAS) inhibitors, Sodium-Glucose Cotransporter 2 inhibitors(SGLT-2i), statins and metformin as first-line treatment. For patients at high risk for CKD progression and CVD events, aldosterone receptor antagonists are recommended. The reduction of urinary protein can be used as a sign of effective treatment. A short-term decrease in urinary protein of about 30% after initiation of RAAS inhibition is a better sign for prognosis in patients with CVD and CKD¹⁴.

1.2 Evaluation of renal function

Based on eGFR and proteinuria levels, the KDIGO guidelines divide CKD into 5 eGFR levels and 3 proteinuria stages (Figure 1) to judge the prognosis of patients. eGFR is one of the reliable indicators to reflect renal function, but its clinical use has certain limitations. Firstly, eGFR is calculated based on serum creatinine levels, which are affected by a variety of

factors, including muscle mass, extrarenal excretion, and dietary factors. Secondly, the eGFR formula is established based on population data and is not applicable to all kidney diseases. Furthermore, the presence of CKD as judged by eGFR alone means that 50% of kidney function has been lost¹⁶.

CKD Category				Classification of Albuminuria		
				A1	A2	A3
				Normal and slightly elevated	Moderately elevated	Severely elevated
				<30 mg/g <3 mg/mmol	30-299mg/g 3-29 mg/mol	≥300mg/g ≥30mg/mmol
Classification of eGFR (ml/min/1.73m ²)	G1	Normal renal function	≥90			
	G2	Mild decline	60-90			
	G3a	Mild to moderate decline	45-59			
	G3b	Moderate to severe decline	30-44			
	G4	Severe decline	15-29			
	G5	Renal failure	15			

Figure 1. Classification and prognosis of chronic kidney disease (CKD) according to the 2012 KDIGO guidelines

UACR is a guideline recommended indicator for monitoring the risk of early kidney injury in T2DM and kidney related diseases, which can reflect early kidney disease and kidney injury. UACR measures the ratio of albumin to creatinine in a single urine sample and is a reliable method for monitoring urinary protein excretion¹⁷. UACR between 30 and 300mg/g is defined as microalbuminuria, and UACR >300mg/g is defined massive proteinuria. UACR can reliably reflect the 24-hour urinary protein volume, and is fast, simple, and accurate. It

is an ideal clinical indicator for qualitative and quantitative diagnosis of albuminuria¹⁸. Thus, given the high cost of CKD treatment and the low cost of detecting albuminuria, as well as the need to identify previously unrecognized patients at high CVD risk, the 2021 ESC Cardiovascular Prevention guidelines recommend that systematic evaluation of urinary protein be considered in all men older than 40 and all women older than 50 (or postmenopausal)¹⁴.

1.3 Improve the awareness rate of kidney disease in CVD patients

However, awareness of CKD has remained low¹⁹. An international cohort of 3 million patients with diabetes or hypertension found that the overall UACR detection rate for diabetes and hypertension was only 35.1% and 4.1%²⁰. A recent Swedish study found that among more than 50,000 patients who met diagnostic criteria for CKD (i.e., at least two eGFR < 60 mL/min/1.73m² separated by more than 3 months), only 23% of patients had a diagnosis of CKD in their electronic health records²¹. The NHANES study found that the awareness rate of CKD is much lower than that of hypertension and diabetes²². In a NHANES study, the awareness rate of CKD patients with severe renal function decline was 41.8%, while the awareness rate of CKD patients with mild to moderate renal function decline was only 7.8%²³. In the KEEP study, the awareness rates of patients with the above two conditions were 32.1% and 5.4%, respectively²⁴. More importantly, patients with eGFR>60 mL/min/1.73 m² and elevated urinary protein account for more than 40% of CKD patients, but urinary protein detection rates were low, and physicians and patients are more aware of this type of CKD²⁵. This missed diagnosis may have adverse consequences for

patient care, as the use of nephrotoxic drugs is more common in undiagnosed CKD patients²⁶. Therefore, in the Healthy People 2030 plan in the United States, improving the awareness rate of CKD continues to be listed as a priority national public health goal by the health department²⁷.

In China, the prevalence of albuminuria measurement in CVD patients is still unclear, and there is limited data on the prevalence of albuminuria in patients with T2DM in the Department of Cardiology. Further research is needed to increase relevant data to better guide the diagnosis and treatment of CVD patients.

2. Research objectives

2.1 Primary objective

To assess the prevalence of albuminuria in patients who are combined with T2DM and different cardiovascular diseases in inpatient and outpatient cardiology departments of secondary and tertiary hospitals in China.

2.2 Secondary objectives

(1) To evaluate the levels of microalbuminuria and macroalbuminuria of patients with type 2 diabetes mellitus (T2DM) in inpatients and outpatients cardiology departments;

(2) To evaluate the prevalence of microalbuminuria and macroalbuminuria in patients with T2DM complicated with different cardiovascular diseases;

(3) To evaluate the related influence factors of albuminuria and the treatment patterns of CKD patients and non-CKD patients in cardiology departments;

(4) To evaluate the management of risk factors and complications in cardiovascular

departments of patients with T2DM complicated with microalbuminuria and macroalbuminuria in different levels of hospitals.

2.3 Exploratory objective

To evaluate the prevalence of retinopathy in T2DM patients with different cardiovascular diseases attending inpatient and outpatient cardiology departments in secondary and tertiary hospitals in China.

3 Research design

3.1 Overall design

The PLACARD study was a cross-sectional observational study.

3.2 Center distribution

In the 6 major administrative regions of China (North China, East China, Northeast China, Central South China, Southwest China, Northwest China), 30 regionally representative medical centers with more than 50 daily outpatients in the Department of Cardiology were selected, among which 3 tertiary hospitals and 2 secondary hospitals in each district. According to the comprehensive situation of the hospital, a representative cardiology ward will be selected in the inpatient department of each branch center, and several representative outpatient doctors will be selected in the outpatient department.

3.3 Number of subjects

In this study, 50 patients with T2DM who meet the inclusion and exclusion criteria in the outpatient department of cardiology and 50 inpatients will be continuously included in each sub-center. A total of 100 patients will be included in each sub-center, totaling 3,000

patients. For details on sample size, see 6.6 Sample Size Estimation.

3.4 Estimated study duration

Each sub-center was activated and enrolled in sequence, with the enrollment period from December 2023 to June 2024.

3.5 Patient Participation Time

Patient data will be collected after signing the informed consent, and the data of enrolled patients will be included in the data analysis. No follow-up will be conducted in this study.

3.6 End of study

The study end date is the enrollment date of the 3,000th patient, which is expected to be completed in June 2024.

3.7 Study Population

This study will adopt a stratified, multi-level, and multi-center strategy for continuous screening to enroll patients who meet all inclusion criteria and none of the exclusion criteria.

During the enrollment period, the Clinical Coordinator will communicate with and invite all potential patients attending the selected inpatient wards or the designated outpatient physicians. Screening information, including patient name, gender, age, screening time, successful enrollment, and reasons for enrollment failure, will be recorded using the patient screening form (see Appendix 1). The patient screening form is kept by each sub-center, which is the source document of this study and must not be transmitted to anywhere outside the sub-center. Before conducting any study procedures or questionnaires, the research team will obtain electronic or written informed consent from patients.

3.7.1 Inclusion criteria

1. Age \geq 18 years old;
2. Diagnosed T2DM combined with \geq 1 CVD (hypertension, coronary heart disease, atrial fibrillation, heart failure);
3. During the data collection period, they went to the outpatient clinic of the cardiology department of the research center, or received treatment in the cardiology department;
4. Ability to self-sign informed consent (electronic /paper).

3.7.2 Exclusion criteria

1. Pregnant or lactating women;
2. Dialysis patients;
3. There are other diseases that lead to elevated proteinuria, such as severe infection, confirmed primary glomerular disease, etc.;
4. Malignant tumors being treated (surgery, chemotherapy, radiotherapy or targeted therapy);
5. Cachexia (CSS score \geq 5 points) ;
6. Severe liver disease (Child- Pugh grade C) ;
7. Participated in an interventional clinical trial in the past three months.

4 Research plan

4.1 Study data collection plan

The PLACARD study will be a cross-sectional observational study that collect patient information only once after screening and retrace the case system after the first visit, without any follow-up. It is expected that each center will complete the screening and

enrollment of patients within one month.

During the information collection period the investigator will:

1. Sign the informed consent form: Before signing the informed consent form, the participants should be fully informed of the research purpose and how the data will be used, and the researcher should also sign the informed consent form. The investigator and the patient each keep an original signed informed consent form;

2. Patient screening form: After signing the informed consent form, it will be confirmed whether the patient meets all the inclusion criteria and not all exclusion criteria, and the screening information will be recorded in the patient screening form. In order to ensure the continuity of screening, the screening information of potential patients who failed to enroll will also be recorded in the patient screening form;

3. After the patients are enrolled, the researchers should complete the following tasks and collect relevant data:

- Demographic information: gender, date of birth, education, type of medical insurance;
- Patient history: T2DM, hypertension, hyperlipidemia, coronary heart disease, atrial fibrillation, heart failure, stroke (ischemic and hemorrhagic), transient ischemic attack (TIA), cataracts, and macular degeneration;
- History of surgical intervention: coronary intervention, coronary artery bypass grafting and coronary angiographic stenosis;
- Questionnaire: Edinburgh Intermittent Claudication Questionnaire (ECQ) ;
- Physical examination: blood pressure, heart rate, height and weight;
- Clinical assessment information: blood glucose (including HbA1c , fasting blood glucose,

two-hour postprandial blood glucose), renal function (including serum creatinine glomerular filtration rate, UACR), blood lipids (including total cholesterol, LDL cholesterol, HDL Cholesterol, triglycerides), funduscopy, and the detection frequency of the above inspections in the past year (mainly based on patient self-report);

- Whether the doctor prescribes urine routine examination for inpatients, and whether the doctor issues a new doctor's order after the outpatients report back the renal function examination;
- Combined drug information: this prescription drug and commonly used drugs (outpatients) and medications during hospitalization (inpatients);
- Information about patient behavior: smoking history and drinking history;
- UACR value detected on the day of enrollment;
- The result of funduscopy gained on the day of enrollment.

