UACR measurement equipment provided in this study to obtain the results. When all the research-related information of the enrolled patients is collected, and the UACR results are obtained and fed back to the doctors, the data collection process is deemed to be over. In addition, after the doctor obtains the results of the UACR examination, whether to revise the doctor's order based on the detected nephropathy is also one of the ways to measure the doctor's awareness of the identification and management of the nephropathy of diabetic patients in the cardiology department.

Flowchart 1, Outpatient enrollment process

Flowchart 2, Inpatient enrollment process

5 Research evaluation

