5.4 Physician behavior and kidney disease management

After collecting the urine sample and calculating the UACR value, the patient will feed back the test results to his/her doctor. This study will record the doctor's current diagnosis, and use the method of reviewing medical records to evaluate whether he/she provides a new diagnosis and prescription for the patient's renal function.

6 Statistical Considerations

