6.3 Outcome Analysis

6.3.1 Main endpoint

The primary endpoint of this study will be the prevalence of albuminuria (UACR \geq 30 mg/g) in patients with type 2 diabetes presented to the Department of Cardiology , and the prevalence of albuminuria and other demographic characteristics will be assessed by descriptive abstracts. In summary, the relationship between the stage of renal impairment/disease (A1-A3 or GFR classification) and relevant covariates was analyzed by logistic regression model. Crude ORs and multivariate-adjusted ORs will be reported, including covariates including:

Age group (18-39 years old, 40-59 years old, 60-69 years old, \geq 70 years old); gender; BMI group (18.5, 23.9, 27.9, 28), blood pressure, blood lipid (LDL, HDL, TG), living habits (smoking, drinking); sub-research centers, nephrotoxic drugs being used, disease history.

Prevalence will be analyzed grouped by stratification factors, gender and age, geographic

region (East, South, Central, North, Northwest and Southwest), etc.

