6.4.2 Secondary endpoints

(1) Albuminuria level in patients with T2DM in the Department of Cardiology (microalbuminuria means UACR value >30 and <300 mg/g; macroalbuminuria means UACR value ≥ 300 mg/g);

(2) The prevalence and level of albuminuria in different types of cardiovascular diseases in the Department of Cardiovascular Medicine (microalbuminuria refers to UACR values >30 and <300 mg/g ; macroalbuminuria refers to UACR values ≥ 300 mg/g);

(3) Different treatment patterns for patients with CKD and patients without CKD;

(4) Assessing the current status of disease-related risk factor management in patients with T2DM attending cardiovascular medicine departments at different levels of hospitals;

(5) Evaluating the management of complications in patients with T2DM in different levels of hospitals.

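### The drug item in Section 4.1 does not separate treatment before the study's UACR result from treatment ordered after it, so the CKD versus non-CKD treatment comparison can include prescribing that the study prompted

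*Protocol*

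**What the plan says.** - **Drug data.** Section 4.1 lists "this prescription drug and commonly used drugs (outpatients) and medications during hospitalization (inpatients". No point in time relative to the UACR result is given.
- **Source of the UACR.** Under Section 4.3, a UACR that the doctor has already ordered is recorded. If none was ordered, staff use the "UACR measurement equipment provided in this study to obtain the results". Section 4.1 dates the value to the day of enrollment.
- **Feedback.** Section 5.4 states: "After collecting the urine sample and calculating the UACR value, the patient will feed back the test results to his/her doctor". Section 4.3 treats data collection as finished once all the information has been gathered and "UACR results are obtained and fed back to the doctors".
- **Response to feedback.** Section 5.4 uses record review to "evaluate whether he/she provides a new diagnosis and prescription for the patient's renal function". Section 4.3 counts a revised order as a measure of the doctor's awareness. Section 4.1 has a separate outpatient item: "whether the doctor issues a new doctor's order after the outpatients report back the renal function examination". The inpatient half of that bullet asks only whether routine urinalysis was ordered.
- **Use of the data.** Secondary endpoint 3 in Section 6.4.2 is "Different treatment patterns for patients with CKD and patients without CKD". Endpoints 4 and 5 cover risk-factor and complication management by hospital level. The logistic models in Section 6.3.1 include "nephrotoxic drugs being used" as a covariate.

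**The concern.** Secondary objectives 3 and 4 are meant to describe how cardiology departments treat these patients in ordinary practice. The study, however, creates information that the doctor may not have had, delivers it, and expects that some doctors will act on it. If the drug record runs past that moment, part of the recorded treatment is a response to the study.

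The error would not fall evenly. Feedback singles out patients with albuminuria, so added prescribing would collect in the group more likely to be classed as CKD and would widen the contrast in endpoint 3. For endpoints 4 and 5 it would also differ by hospital level if doctors at different levels respond differently to the result, which the protocol does not address.

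This is a matter of data capture. If the case report form does not date drugs against the result, no later analysis rule applied to the form data can separate the two kinds of prescribing.

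**Working it through.** **Step 1: reading the timing rules together**

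- *Outpatients.* The current prescription belongs to the visit at which the result may come back. The usual-drugs item largely describes earlier treatment. The new-order item records whether an order was issued and names no drug, so a new drug cannot be subtracted from the current prescription.
- *Inpatients.* Medication during the stay has no stated end point, and Section 4.1 has no post-feedback order item for them. Section 3.3 plans 50 inpatients in each of 30 centers: 50 × 30 = 1,500 of 3,000.
- *End of collection.* The closing rule in Section 4.3 has two conditions, complete information and feedback given. It says when a record is finished and sets no cut-off for drugs. It also sits badly with the observation after feedback that Sections 4.1, 4.3 and 5.4 require.

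The plan therefore permits post-feedback drugs in the comparison without stating that they are in it.

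**Step 2: size**

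The protocol has no figure on this point. Its one design figure (Section 6.6) reproduces: 1.96 × √(0.25/3000) = 1.79 points, so 48.2% to 51.8%, width 3.6 points. The present point does not depend on it.

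Assumptions, none from the protocol:

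- 1,500 patients per group, which follows the 50% planning prevalence if CKD is classified from the study UACR.
- Use of a drug class before feedback is p in both groups, so there is no true difference.
- A share u of the CKD group has a study-generated UACR.
- A share q of the untreated among them start the drug after feedback, and the start is recorded.

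Recorded use in the CKD group: p₁ = p + (1 − p) × q × u. False difference: (1 − p) × q × u.

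OR = [p₁/(1 − p₁)] / [p/(1 − p)].

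Half-width of the 95% CI for the difference, ignoring clustering: 1.96 × √[p₁(1 − p₁)/1500 + p(1 − p)/1500].

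| p | q | u | False difference (points) | OR | Half-width (points) |
|---|---|---|---|---|---|
| 0.6 | 0.05 | 0.5 | 0.4 × 0.05 × 0.5 = 1.0 | 1.04 | 3.5 |
| 0.4 | 0.05 | 0.9 | 0.6 × 0.05 × 0.9 = 2.7 | 1.12 | 3.5 |
| 0.4 | 0.10 | 0.5 | 0.6 × 0.10 × 0.5 = 3.0 | 1.13 | 3.5 |
| 0.4 | 0.10 | 0.9 | 0.6 × 0.10 × 0.9 = 5.4 | 1.25 | 3.5 |
| 0.2 | 0.20 | 0.9 | 0.8 × 0.20 × 0.9 = 14.4 | 2.10 | 3.1 |

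Over the full grid (p = 0.2, 0.4, 0.6; q = 0.05, 0.10, 0.20; u = 0.5, 0.9) the false difference runs from 1.0 to 14.4 points and exceeds its own half-width in 11 of 18 cells. At q = 0 it is zero.

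The only anchor for u in the protocol is the 35.1% UACR detection rate in diabetes cited in Section 1.3 from an international cohort. If it carried over, u = 1 − 0.351 = 0.649. With p = 0.5 and q = 0.10 the false difference is 0.5 × 0.10 × 0.649 = 3.2 points (OR 1.14). With q = 0.20 it is 6.5 points (OR 1.30).

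**The case against.** The strongest reply is that the protocol nowhere puts post-feedback prescriptions into the CKD comparison. Section 4.1 collects data once without follow-up, Section 4.3 closes collection at feedback, and Sections 4.3 and 5.4 assign revised orders to the assessment of physician behavior. The form and the analysis plan, which are not shown, may carry the time fields. The enrollment flowcharts, which might show the order of steps, are also missing from the text. Much of this stands, and it rules out several stronger readings that a reader might infer:

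- *That the study does create part of the difference it reports.* The timing is left open, so only the possibility is supported.
- *That nothing recorded for inpatients precedes the result.* Section 5.1 lists drug history for enrolled patients, and an in-hospital drug list includes orders from before the urine sample. The defect is that earlier and later orders are not separated.
- *That outpatient drugs are recorded again the next day.* Section 4.3 gives that query the purpose of filling gaps.
- *That the drug covariate in Section 6.3.1 is shown to follow the outcome.* It concerns nephrotoxic drugs. Finding albuminuria would hardly prompt starting one, and stopping one would not remove it from a list of drugs given during the stay.

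The mechanism is also confined to patients whose doctor had not already ordered a UACR. It is direct only where CKD status rests on the study UACR: Section 4.2 does not define CKD, and Section 6.3.1 also refers to GFR classes.

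The reply does not supply a cut-off. The closing rule is not one, and the separate order item covers outpatients only and names no drug.

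**Conclusion.** The point holds in limited form. For patients with a study-generated UACR, the plan can be followed exactly and still yield a treatment comparison that includes prescribing prompted by the study. Inpatients are the clearest case.

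The size is unknown. The range of roughly 1 to 14 percentage points rests on assumed start rates of 5% to 20%, equal prior use in both groups, and CKD classified from the study UACR. At the lower end the effect lies within sampling error; at the upper end it would look like a real treatment pattern.

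The primary endpoint, prevalence of UACR of at least 30 mg/g, is untouched. The affected endpoints are secondary and descriptive, and Section 6.6 states no pre-defined hypothesis tests. The change is worth making because it is cheap and cannot be recovered from undated form data.

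**What to change.** - In Section 4.1 and the case report form, time-stamp drug orders against feedback of a study-generated UACR, for inpatients as well as outpatients.
- For endpoints 3 to 5 in Section 6.4.2, use drugs in use or ordered before feedback. This includes the visit's prescription if it was written before the result, and inpatient orders up to feedback.
- For the drug covariate in Section 6.3.1, use drugs in use before the urine sample.
- Report orders made after feedback only under the physician-behavior evaluation in Section 5.4.
- Reconcile the end of data collection in Section 4.3 with the new-order item in Section 4.1, the next-day record query in Section 4.3 and the record review in Section 5.4.

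The cost is slightly more abstraction of order times from the hospital information system, which staff already query under Section 5.2. No sample-size figure changes.
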